## 2.7. Specimen collection, storage and shipping

Serum will be collected for measurement of serum creatinine and subsequent calculation of creatinine clearance to determine if the participant meets the eligibility criteria.

Biospecimens collected for measurement of serum zinc and copper levels will be processed at the clinical sites and sent to Quest Diagnostic laboratories, a CLIA approved central laboratory, for zinc and copper assessment. Zinc assessment will be measured to assess whether serum zinc levels are associated with cough and response to treatment, and whether supplementation increases serum zinc levels. Copper assessment will be performed to check for signs of potential copper deficiency. Participants should fast for at least 4 hours prior to collection of blood for zinc and copper analysis. Specimens for serum zinc and copper analysis must be processed within 2 hours to ensure accurate assessment of zinc and copper levels.

Additional blood will be collected and stored for future use. The ALA-ACRC maintains a biorepository of specimens from our studies to conduct ancillary studies of the relationship of biomarkers to airway and related diseases. Permission to draw and store biospecimens for future ancillary studies and/or DNA testing is optional and is not a requirement for participation in this study. The results of future genetic testing will not be provided to study participants. Blood specimens for future use are stored at -70° or -80° C at the local site and shipped periodically in batches on dry ice for storage at the ACRC biospecimen repository at Nemours Children's Center (NCC). The DCC supplies blood drawing tubes, bar-code labels, shipping labels, containers, and transmittal slips. All sites are required to be certified in biosafety for handling biological specimens in accordance with local hospital / university policy and applicable law.

## 3. Study treatment

---

### 3.1. Description of study treatment

Participants will be randomly assigned to receive a daily dose of 150 mg of zinc acetate or matched placebo taken in three doses of 50 mg each or placebo. For this trial 50 mg zinc acetate capsules will be over-encapsulated and a matched placebo will be created. Zinc will be taken with the morning or evening meal. Participants will be instructed to titrate up the dose of study drug starting with one capsule (50 mg) in the morning on day 1, increasing to two capsules (100 mg) on day 4, and reaching three capsules (150 mg) on day 8. Participants will be instructed to take the medication with food. If participants are not able to tolerate the full dose, they may split the dose

into two or three doses per day taken at meal-time (e.g. two capsules in AM and one capsule in PM, or one capsule with breakfast, lunch, and dinner). If a participant is not able to tolerate the full dose, then the dose should be titrated down to the highest tolerable dose, i.e., one or two capsules as tolerated.

The study will use the FDA-approved formulation of oral zinc, Galzin®. FDA has approved Galzin® 150mg/day for long-term use in adults with Wilson's disease. Zinc supplementation for food has been considered Generally Recognized as Safe (GRAS) by the FDA. NIH recommends up to 40 mg/day as a dietary supplement in adults and multivitamins used long-term for prevention of macular degeneration contain 80mg of elemental zinc. OTC lozenges (Cold-eez®) contain 13.3 mg of zinc as zinc gluconate and are taken in doses of up to 80 mg/day for relief of URI symptoms. Zinc gluconate is available as unregulated nutritional supplements in 100mg capsules.

### 3.2. Randomization

Participants will be randomized to zinc acetate or placebo at V2. Treatment assignment will be randomly allocated in a 1:1 ratio with stratification by clinic with permuted block design will be used. Assignments will be released from the DCC after evidence that an eligible participant has signed consent and completed all baseline evaluations.

Zinc acetate or placebo will be dispensed to the participant at the V2 visit. At randomization the participant will be assigned a unique bottle ID code and clinics will dispense that bottle to the participant. Each participant will receive a single bottle of 168 capsules for the 6 weeks of treatment. At the second to last study (V5) visit, the bottle with the unused capsules will be returned.

### 3.3. Side effects

The most common adverse effects of zinc supplementation are dyspepsia, nausea, and a metallic taste. These side effects can be mitigated by downward adjustment of the dose, taking the drug with meals, and/or spreading the dose out over the day (i.e. taking 1 capsule in the morning and 2 capsules at night, or taking 1 capsule each at breakfast, lunch, and dinner).

Elevations of liver and pancreatic enzymes have been reported in patients with Wilson's disease, treated with zinc acetate, but this has not been reported in other populations and the relationship with zinc supplementation is unclear. Participants with a history of pancreatitis will be excluded from the study. Study participants experiencing abdominal pain should be evaluated for possible pancreatitis. With zinc gluconate nasal spray some patients have noted loss of smell, but this has not been reported with oral zinc.

Zinc is listed as a class A drug for pregnancy indicating that it does not have substantial teratogenic potential. We are excluding pregnant and lactating women from this trial because pregnancy may have either beneficial or deleterious effects on chronic cough and zinc is transmitted in breast milk that may alter infant feeding behavior. Women of child bearing potential must be willing to use appropriate methods of pregnancy prevention during the duration of the study. Women of childbearing potential includes all female participants except those who are surgically sterile (both ovaries and/or uterus removed), postmenopausal (no menstrual period for longer than 12 consecutive months), or incapable of pregnancy.

The FDA-approved prescribing information for zinc acetate states the following regarding over-dosage:

"One fatality associated with over-dosage of zinc sulfate has

Confidential, not for attribution or citation.

been reported. The death of this adult woman followed the accidental ingestion of approximately 28 g of zinc sulfate. [Equivalent to 560 capsules of zinc acetate or 3 bottles of dispensed study drug]. Death occurred on the fifth day after ingestion and was attributed to renal failure. Hemorrhagic pancreatitis and hyperglycemic coma resulted from the overdose. The amount ingested was 500 mg/Kg of zinc sulfate, a value that is in the same order of magnitude as that found to be lethal in animals.”

Drug interaction information contained in UpToDate indicates that absorption of the following medications might be impaired by zinc: cephalosporin antibiotics, quinolone antibiotics, tetracycline antibiotics, bisphosphonates, dolutegravir, deferiprone, and eltrombopag. If a participant is prescribed one of these medications during the study, the participant will be instructed to take zinc/placebo at least 1 hour prior to or 1 hour after taking that medication.

In theory, prolonged consumption of zinc could lead to copper deficiency which is manifest as a reversible anemia and neutropenia as well as neuropathy. Because copper is ubiquitous in the diet, and deficiency is rare in the absence of malabsorption syndromes or gastric bypass surgery, it is unlikely that the duration of treatment in this trial will lead to copper deficiency. However, in patients using long-term high-dose zinc, monitoring for hematologic abnormalities and peripheral neuropathy would be indicated. We will measure serum copper levels prior to starting study drug and after completing study drug treatment to assess for potential signs of copper deficiency, as well as to assess the likelihood of side effects in more long-term use of zinc.

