### 2.1. Trial schema

### 2.2. Eligibility criteria

Participants must affirm that they have multiple daily episodes of cough that have persisted for more than three months. Individuals with asthma/eosinophilic airway disease or gastroesophageal reflux may be eligible if treatment with inhaled corticosteroids and/or bronchodilators, or H2 blockers and/or proton pump inhibitors, respectively, did not resolve cough. In addition, individuals with upper airway cough and/or rhinosinusitis whose cough did not respond to nasal steroids, antihistamines and/or expectorants/decongestants may be eligible to participate.

Individuals on treatments for cough (e.g. inhaled corticosteroids, H2 blockers, nasal steroids) should remain on their background treatment during the trial.

Individuals cannot be current smokers (not smoked for at least six months), cannot be using an ACE inhibitor, and cannot have any parenchymal lung disease as all of these can cause cough.

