**Exclusion criteria:**

- Marijuana use (smoking or ingestion of marijuana) in the past 6 months
- Use of ACE inhibitor currently or within the past 6 weeks
- Use of zinc supplements or multivitamins containing zinc currently or within the past 6 weeks
- Occupational exposure to dust or chemicals that may cause cough, as determined by study physician
- Diagnosis or evidence of COPD (FEV1/FVC < 0.70 and FEV1% predicted < 80%)
- History of:
  - Bronchiectasis
  - Interstitial lung disease
  - Sarcoidosis
  - Pneumoconiosis
  - Asbestosis

- Chronic mycobacterial infection
- Lung cancer
- Pancreatitis
- Congestive heart failure
- Chronic kidney disease (creatinine clearance < 30mL/min)
- Pregnant or breast-feeding
- Other medical conditions that would interfere with participation in study

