## 2.4. Summary of visits

### Visit 1 Screening Visit (week -1, 2 hours)

- Consent
- Eligibility assessment
  - Chest x-ray, if participant does not have chest x-ray or CT from within the past 2 years
- Cough Visual Analog Scales (C-VAS)
- Baseline medical history
- Spirometry (pre- and post-bronchodilator)
- Pregnancy test for women of child-bearing potential
- Blood draw for creatinine level, serum zinc and copper levels, and biospecimens
- Explain and distribute cough diary

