### Visit 2 Baseline / Randomization (week 0, 2 hours)

- Interval medical history
- Collect and review cough diary
- Cough questionnaire completion
  - Cough Visual Analog Scales (C-VAS)
  - Cough Quality of Life Questionnaire (CQLQ)
  - Leicester Cough Questionnaire (LCQ)
  - Global Assessment of Change in Cough (GACC)
  - Cough-related Impact on Quality of Life Scale (Cough IQOLS)
  - EQ-5D
- Physical examination
- Eligibility review and randomization
- Dispense study treatment

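### The 1-hour spacing rule for medicines whose absorption zinc may impair is written for new prescriptions and does not expressly reach participants already taking one at entry

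*Combined protocol and SAP*

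**What the plan says.** Section 3.3 (Side effects), citing a drug-information source, states that "absorption of the following medications might be impaired by zinc: cephalosporin antibiotics, quinolone antibiotics, tetracycline antibiotics, bisphosphonates, dolutegravir, deferiprone, and eltrombopag". It then gives one instruction under one condition. The condition is "If a participant is prescribed one of these medications during the study"; the instruction is that "the participant will be instructed to take zinc/placebo at least 1 hour prior to or 1 hour after taking that medication".

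Other sections bear on medicines in use at entry:

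- **Section 2.2, opening text.** People on cough treatments "should remain on their background treatment during the trial". Other background medicines are not mentioned.
- **Section 2.2, exclusion criteria.** The substances whose current or recent use excludes a person are ACE inhibitors ("Use of ACE inhibitor currently or within the past 6 weeks"), zinc-containing products and marijuana. The catch-all is "Other medical conditions that would interfere with participation in study", which is about conditions and not medicines.
- **Section 2.4.** Visit 1 includes "Baseline medical history" and Visit 2 includes "Eligibility review and randomization", followed by dispensing. The week-1 call goes over study procedures and adherence.
- **Section 2.6.3.** Medication use is among the clinical data assessed.
- **Section 3.1.** Study drug is taken with food, at one to three dosing times a day. Separation from other medicines is not mentioned.

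**The concern.** The rule exists because zinc may reduce the absorption of certain medicines. That reason applies equally whether the medicine was started before or after enrolment, and the plan gives no ground for treating the two cases differently. The participant left out may have the longer exposure: someone already on a listed medicine can overlap with zinc for all 6 weeks of treatment, whereas someone prescribed it part-way through overlaps only for the time remaining. Several of the listed medicines, bisphosphonates and dolutegravir for example, could well be in use at entry.

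At stake is possible under-absorption of a participant's other medicine because the plan's own precaution was not passed on. The documents give neither the size nor the clinical consequence of the interaction. Sample size, power, endpoints and analysis are unaffected.

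**Working it through.** This is mainly a check of wording. The plan states no figure to reproduce.

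**Step 1. Who receives the instruction?** The spacing rule appears once in the visible text, in section 3.3, with a trigger tied to prescribing during the study.

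**Step 2. Does any other text exclude or instruct current users?**

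| Section | What it covers | Reaches a current user of a listed medicine? |
|---|---|---|
| 2.2 opening text | Staying on background cough treatment | No |
| 2.2 inclusion criteria | No respiratory infection in the previous 4 weeks | Makes antibiotic use at entry less likely; does not bar it, and does not address the four non-antibiotic items |
| 2.2 exclusion criteria | ACE inhibitors, zinc products, marijuana, named and other medical conditions | No |
| 2.4 Visits 1 to 3 | History, eligibility review, procedures, adherence | Gives the opportunity, but does not refer to the list |
| 2.6.3 | Medication use assessed | No action attached |
| 3.1 | Food and dose-splitting advice | No |
| 3.4 | Wallet card stating trial participation | No |

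No row closes the gap.

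**Step 3. How much of the day does the rule cover?** Inputs: 1 hour either side of a dose (section 3.3), and one, two or three dosing times a day (section 3.1). Assumption: dosing times are at least 2 hours apart.

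- Window per dosing time = 1 h + 1 h = 2 h
- One dosing time: 1 × 2 = 2 h; 2/24 = 8.3%
- Two dosing times: 2 × 2 = 4 h; 4/24 = 16.7%
- Three dosing times: 3 × 2 = 6 h; 6/24 = 25.0%

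These are the hours in which the rule would matter. They are not the probability that two medicines are taken together. A listed medicine taken outside the window is already separated. Section 3.1 offers divided dosing largely for people who do not tolerate the full dose at once, so the larger figures are upper cases.

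**Step 4. How many people?** The documents give no prevalence of listed medicines, and none is assumed here. With 36 participants allocated 1:1, about half of any affected group would receive zinc.

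**The case against.** The strongest counter-argument is linguistic. A person holding a continuing prescription is, in one sense, prescribed that medicine while on study, and the sentence follows directly after the interaction list, so its purpose is plain. Site staff who know the list and find a listed medicine at V1 or V2 have no reason to withhold the advice. That reading is possible, but the text does not state it, and three centers should not have to infer a safety instruction.

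Second, the natural home for such advice may be out of sight. The consent pages were removed before review, the appendix shows only its heading, and a manual may exist. This stands as a limit: the finding concerns the visible text only.

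Third, the numbers are small. Three of the seven listed items are antibiotic classes, which the 4-week infection criterion makes less likely at entry. The exclusion for other medical conditions gives some discretion over the diseases for which the remaining items are taken. Histories and adverse-event reviews at later visits, and the wallet card, are further occasions for a concurrent medicine to surface. All of this lowers the importance of the point. None of it gives the instruction to a current user.

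Finally, the daily-window percentages measure neither people affected nor harm. That is correct, and they should not be read that way.

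**Conclusion.** The concern holds on the visible text. The plan states a specific precaution with a trigger that is too narrow on its ordinary reading, and it leaves out a group with the same interaction and possibly longer exposure.

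It is a minor participant-safety point, worth considering and not a threat to the trial. The number affected is unknown and probably small; the exposure is up to 6 weeks; and the rule would bear on 2 to 6 hours of the day depending on how the dose is split. The conclusion rests on two assumptions: that the trigger means a prescription made after entry, and that the removed consent pages or a manual do not already give the instruction. Confidence is moderate for those reasons.

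**What to change.** Reword the trigger in section 3.3 so that it covers anyone taking a listed medicine at enrolment as well as anyone prescribed one later. Add one line to the V1 and V2 procedures to check current medicines against the list. Give the spacing instruction when study drug is dispensed at V2, and repeat it at the week-1 call (V3) for anyone affected. If a consent form or manual already says this, bring section 3.3 into line with it.

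The cost is a few words and a brief check, using medication information that the trial already assesses. The existing instruction applies to zinc and placebo alike, so masking is kept. Eligibility and analysis do not change.

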**Visit 5 On-treatment final follow-up visit (week 6, 2 hours)**

- Interval medical history
- Assess for adverse events
- Collect and review cough diary
- Spirometry (pre- and post-bronchodilator)
- Cough questionnaire completion
  - Cough Visual Analog Scales (C-VAS)
  - Cough Quality of Life Questionnaire (CQLQ)
  - Leicester Cough Questionnaire (LCQ)
  - Global Assessment of Change in Cough (GACC)
  - Cough-related Impact on Quality of Life Scale (Cough IQOLS)
  - EQ-5D
- Drug return
- Blood draw for serum zinc and copper levels

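### Two conditions that section 3.3 ties to copper deficiency are not named exclusions, and the screening copper result has no eligibility cut-off before dispensing

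*Combined protocol and SAP*

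**What the plan says.** Section 3.3 (Side effects) discusses copper deficiency as a theoretical result of prolonged zinc intake and lists anemia, neutropenia and neuropathy as its signs. It considers deficiency unlikely over the trial's treatment period. The grounds are that copper is plentiful in the diet, that "deficiency is rare in the absence of malabsorption syndromes or gastric bypass surgery", and that treatment is short. It adds that copper will be measured before and after treatment.

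The exclusion list in section 2.2 names pancreatitis, heart failure, chronic kidney disease and several lung diseases. It names neither malabsorption nor gastric bypass. The last item is general: "Other medical conditions that would interfere with participation in study".

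Visit 1 in section 2.4 includes "Blood draw for creatinine level, serum zinc and copper levels, and biospecimens". Section 2.7 gives creatinine an explicit role: "subsequent calculation of creatinine clearance to determine if the participant meets the eligibility criteria". For copper it gives only the purpose of looking for deficiency. Section 5.2 says the central laboratory determines reference values for zinc and copper, and that results pass between the site, the laboratory and the coordinating center. Visit 2 lists "Eligibility review and randomization", followed by dispensing. The next copper sample is at Visit 5: "Blood draw for serum zinc and copper levels".

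**The concern.** The reassurance in section 3.3 is partly conditional: deficiency is rare when two conditions are absent. A reader would expect the eligibility criteria to make them absent, and the listed criteria do not. The catch-all is a weak substitute because it is worded around taking part in the study. A person with a past gastric bypass could attend every visit and take every capsule, so a site applying the wording literally has no reason to exclude.

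The screening copper value could act as a second safeguard, since it is the only copper measurement before dosing. But the protocol does not say what follows if it is low. A person with one of the two conditions, or with low copper at screening, can therefore be assigned to zinc at 150 mg/day for six weeks unless the site decides otherwise. What is at stake is the safety of a small and unknown number of participants, and whether these criteria are carried into the larger trial for which this is the pilot.

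**Working it through.** The plan gives no figure on this point, so the main check is to set its provisions side by side.

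| Item | Where it is raised | Named exclusion or cut-off | Stated consequence before V2 dispensing |
|---|---|---|---|
| Creatinine | V1 draw; 2.7 | Clearance below 30 mL/min (2.2) | Decides eligibility (2.7) |
| Past pancreatitis | 3.3: enzyme rises in Wilson's disease, link to zinc unclear | Yes (2.2, 3.3) | Excluded |
| Malabsorption or gastric bypass | 3.3, copper paragraph | None | Catch-all only, at site discretion |
| Serum copper | V1 draw; 2.7, 3.3, 5.2 | None | Result goes to the site; no action stated |

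Two things follow. First, the plan already turned one uncertain zinc-related risk (pancreatitis) into a named exclusion rather than leaving it to the catch-all. Naming the two copper-related conditions would follow the same practice. Second, creatinine and copper come from the same V1 draw, but only creatinine has a decision attached.

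**Other safeguards in the text.** Section 3.2 releases the assignment for an eligible, consented participant whose baseline assessments are done. It does not separately ask that the copper result be acted on. The treatment stop in section 3.4 is triggered by adverse events, not by a copper value. The schedule in section 2.5 has no blood count, and its only physical examination is at V2, before dosing.

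**Time between copper values.** V1 is at week -1 and V5 at week 6, so 6 - (-1) = 7 weeks.

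**Exposure between them, on the titration in section 3.1.** One capsule on days 1-3, two on days 4-7 and three on days 8-42, each of 50 mg:

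- Capsules: 3×1 + 4×2 + 35×3 = 3 + 8 + 105 = 116.
- Total dose: 116 × 50 = 5,800 mg.
- Daily mean: 5,800 / 42 = 138.1 mg.
- Days at 150 mg: 42 - 7 = 35.

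These figures describe exposure only.

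**Effect on the design.** Section 4.1 states 80% power for 0.56 SD with 18 per arm and one-sided alpha 0.20. The noncentrality is 0.56 × √(18/2) = 1.68. Power is 79.9% by the normal approximation and 79.7% by the t-test with 34 degrees of freedom, so the stated figure reproduces. No input to it depends on the copper criteria, and the change leaves it as it is.

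**The case against.** The strongest reply is that the conclusion in section 3.3 is about duration. Six weeks is short, copper is common in the diet, and the remark on malabsorption explains why deficiency is rare in general. It does not promise that such people will be absent from the trial. The protocol meets the remaining uncertainty by measuring copper before and after treatment. Sites also take a medical history at V1, examine the participant and review eligibility at V2, and ask about adverse events at weeks 1 and 3. A medical monitor reviews serious or unusual events. A protocol need not list every condition that a study physician would recognize.

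Most of this stands, and it is why the point is minor. It does not supply what is missing, which is a stated exclusion or a stated consequence of a low copper value.

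Three stronger readings are tempting, and the documents do not support them:

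- A reader might infer that nobody looks at copper before dosing. Sections 2.7 and 3.3 say it is measured to look for deficiency, and section 5.2 says the result is shared with the site. The gap is the missing cut-off and action, not missing review.
- A reader might infer that nothing would keep an at-risk person out. History, examination, eligibility review and the catch-all all could. The text of the appendix and the site forms is not in the file, so the point is limited to what the protocol text states.
- A reader might set the dose against the statement that "NIH recommends up to 40 mg/day as a dietary supplement in adults" and infer harm. The ratio would be 150/40 = 3.75 if 50 mg means elemental zinc, and less if it means salt weight. Either way it says nothing about copper over six weeks, and section 3.1 notes that 150 mg/day is approved for long-term use in Wilson's disease.

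**Conclusion.** The point holds as a small eligibility gap. Part of the rationale in section 3.3 depends on the absence of two conditions that the criteria do not name, and the screening copper value has no eligibility cut-off or action before dispensing. It is a cheap improvement to participant safety, not an analysis error: there is no effect on the CQLQ comparison, the sample size or the error rates.

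No probability of harm can be given. The documents contain no prevalence for either condition and no deficiency rate at this dose and duration. Section 3.3 describes the anemia and neutropenia as reversible, and the short treatment limits the risk. The exposure figures assume full adherence to the scheduled titration with no dose reduction. Confidence is high that neither condition is named and that no copper cut-off or action is stated. The documents do not show how often this would matter.

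**What to change.** 1. Section 2.2, exclusion criteria, under the history items: add malabsorption syndrome or gastric bypass surgery.
2. Section 2.4, Visit 2, at the eligibility review: state that a participant whose V1 serum copper is below the central laboratory's lower reference limit is not randomized. A documented review alone would not be enough, because it would leave a low value without a consequence.

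The cost is one history question at V1 and one check at V2, using a sample already drawn and reference values the laboratory already determines. The downside is that a few candidates will be excluded. V2, scheduled one week after V1, may also have to wait for the copper result, whose turnaround time the documents do not give.
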